4.1.3 Follow-up for Toxicities

When treatment is interrupted or permanently discontinued due to an AE or abnormal laboratory value, the patient must be followed at a frequency as medically indicated until resolution or stabilization of the event, whichever comes first. All patients will be followed for AEs and SAEs for at least 30 days following the last dose of pamiparib.

For prolonged hematological toxicities, treatment should be interrupted and blood counts should be monitored weekly until recovery. If the levels have not recovered to NCI-CTCAE \leq Grade 1 or baseline after 8 weeks, the patient should be referred to a hematologist for further investigations, including bone marrow analysis and blood sample for cytogenetics. If MDS/AML is diagnosed, treatment of pamiparib must be permanently discontinued, and the event should be reported as an SAE regardless of causality.

4.1.4 End of Study

The study termination is defined as the time point when data collection for the patient will stop. The study will continue until the last patient has died, becomes lost to follow up, or withdraws from study, or until sponsor decides to terminate the study.

The sponsor has the right to terminate this study at any time. Reasons for terminating the study early may include, but are not limited to, the following:

- The incidence or severity of adverse events in this or other studies indicates a potential health hazard to patients
- Overall patient enrollment is unsatisfactory

The sponsor will notify each investigator if a decision is made to terminate the study. Should this be necessary, prematurely discontinued patients should be seen as soon as possible for an EOT visit and Safety Follow-up visit.

The investigators may be informed of additional procedures to be followed in order to ensure that adequate consideration is given to the protection of the patient's interests. The investigator will be responsible for informing IRBs/Independent Ethics Committees (IECs) of the early termination of the trial.

The sponsor has the right to close a site at any time. The decision will be notified to the site in advance. Reasons for closing a site may include but are not limited to the following:

- Excessively slow recruitment
- Poor protocol adherence
- Inaccurate or incomplete data recording
- Good Clinical Practice (GCP) noncompliance

• Study activity is completed (ie, all patients have completed and all obligations have been fulfilled)]

4.2 Selection of Study Population

4.2.1 Inclusion Criteria

Patients may be enrolled in the study only if they meet all of the following criteria:

- 1. Patients have voluntarily agreed to participate by giving written informed consent
- 2. Age 18 years (including 18 years) on the day of signing informed consent
- 3. Patients meet the following eligibility criteria for the corresponding part of the study:
 - 1) Phase 1 Portion:
 - a) The patients must have a histologically or cytologically confirmed locally advanced or metastatic TNBC, or high-grade, non-mucinous, epithelial ovarian cancer (including fallopian or primary peritoneal cancer) for which no effective standard therapy is available
 - b) *BRCA1* and *BRCA2* mutations are not required but enrichment of this patient population is preferred
 - c) Patients must agree to retrospective germline BRCA testing using blood samples
 - d) Archival tumor tissues will be collected, if available
 - 2) Phase 2 Portion:
 - a) Patients who have histologically or cytologically confirmed high-grade (Grade 2 or Grade 3 endometrioid epithelial cancer is acceptable too), non-mucinous, epithelial ovarian cancer (including fallopian, or primary peritoneal cancer), harboring germline *BRCA1/2* mutation and must meet the following criteria:
 - i. Patients must have received at least 2 lines of standard chemotherapy, currently with relapsed/progressive disease or have withdrawn due to unacceptable toxicity from most recent standard treatment
 - ii. Platinum-sensitive or platinum-resistant patients (Patients are defined as platinum sensitive if disease progression by RECIST, version 1.1, had occurred ≥ 6 months after their last platinum treatment, while platinum-resistant is defined if disease progression occurred < 6 months after the

last platinum treatment

- iii. If mixed histology, >50% of the primary tumor had to be confirmed to be high-grade (Grade 2 or Grade 3 endometrioid epithelial cancer is acceptable too), non-mucinous, epithelial ovarian cancer
- b) All patients will be required to undergo germline *BRCA1/2* mutation testing using blood samples prior to enrolment
- c) Archival tumor tissues will be collected, from all patients, if available
- 4. Patients must have measurable disease as defined per the RECIST, version 1.1
- 5. Eastern Cooperative Oncology Group (ECOG) performance status of ≤ 1 (Appendix 3)
- 6. Life expectancy ≥ 12 weeks
- 7. Patients must have adequate organ function as indicated by the following laboratory values:
 - Absolute neutrophil count (ANC) $\geq 1,500/\text{mm}^3$ or $1.5 \times 10^9/\text{L}$
 - Platelets \geq 75,000/mm³ or 75 x 10⁹/L
 - Hemoglobin \ge 9 g/dL or \ge 5.6 mmol/L

(If transfusion is used, at least 14 days should pass before re-test for hematology is performed at the screening visit)

- Estimated glomerular filtration rate (eGFR) ≥30 mL/min/1.73m² by Chronic Kidney Disease Epidemiology Collaboration Equation (CKD-EPI EQ; Appendix 6)
- Serum total bilirubin ≤ 1.5 x upper limit of normal (ULN)
- Aspartate aminotransferase and alanine aminotransferase $\leq 3 \times ULN$
- 8. Females of childbearing potential and nonsterile males (only for Phase 1), must practice highly effective method of birth control (Appendix 11) for the duration of the study and for at least 6 months after the last study drug administration

4.2.2 Exclusion Criteria

Patients will not be entered in the study for any of the following reasons:

- Patients who have been treated with chemotherapy, biologic therapy, immunotherapy, investigational agent, anti-cancer Chinese medicine, or anti-cancer herbal remedies ≤ 14 days (or ≤5 half-lives, whichever is shorter) prior to starting study drug, or who have not adequately recovered from the side effects of such therapy
- 2. Patients who have undergone major surgery for any cause ≤ 4 weeks prior to starting study drug. Patients must have adequately recovered from the previous treatment and have a stable clinical condition before entering this study

- Patients who have undergone radiotherapy for any cause ≤ 14 days prior to starting study drug. Patients must have adequately recovered from the previous treatment and have a stable clinical condition before entering this study
- 4. Untreated and/or active brain metastases
 - A scan to confirm the absence of brain metastases is not required.
 - Patients with treated brain metastases must be off corticosteroids for ≥ 14 days and have no signs or symptoms of progressive brain metastases
- 5. Prior therapies targeting PARP
- 6. Inability to swallow oral medications (capsules and tablets) without chewing, breaking, crushing, opening or otherwise altering the product formulation.
- 7. Patients with any of the following cardiovascular criteria:
 - Cardiac chest pain, defined as moderate pain that limits instrumental activities of daily living, ≤ 28 days prior to Day 1
 - Evidence of symptomatic pulmonary embolism within 28 days prior to Day 1
 - Acute myocardial infarction ≤ 6 months prior to Day 1
 - Heart failure of the New York Heart Association Classification III or IV (see Appendix 12) ≤ 6 months prior to Day 1
 - \geq Grade 2 ventricular arrhythmia \leq 6 months prior to Day 1
 - Cerebrovascular accident ≤ 6 months prior to Day 1
- 8. Patients with other malignant cancer:
 - Except for surgically excised non-melanoma skin cancer, adequately treated carcinoma *in situ* of the cervix, adequately treated low-stage bladder cancer, ductal carcinoma *in situ* treated surgically with curative intent, or a malignancy diagnosed ≥ 5 years ago with no current evidence of disease and no therapy ≥ 5 years prior to Day 1
- 9. Diagnosis of myelodysplastic syndrome (MDS)
- 10. Known human immunodeficiency virus (HIV) infection, active viral hepatitis, or active tuberculosis
- 11. Use ≤ 10 days (or ≤ 5 half-lives, whichever is shorter), prior to Day 1, or anticipated need for food or drugs known to be strong or moderate CYP3A inhibitors or strong CYP3A inducers (Appendix 8)
- 12. Pregnancy or nursing:
 - Females of childbearing potential require a negative urine or serum pregnancy test ≤ 7 days

before Day 1

- 13. Significant intercurrent illness that may result in the patient's death prior to death from HGOC, or TNBC (only for Phase 1 portion)
- 14. Known history of intolerance to the excipient of the pamiparib capsule
- 15. Previous complete gastric resection, chronic diarrhea, active inflammatory gastrointestinal disease, or any other disease-causing malabsorption syndrome
 - Gastroesophageal reflux disease under treatment with proton pump inhibitors is allowed
- 16. Active bleeding disorder, including gastrointestinal bleeding, as evidenced by hematemesis, significant hemoptysis, or melena ≤ 6 months before Day 1
- 17. Any illness that investigator thinks makes the patient unsuitable for entry into the study
- 18. Unsolved acute effects of prior therapy of \geq Grade 2
 - Except for AEs not considered a likely safety risk (eg, alopecia, neuropathy, and specific laboratory abnormalities)

4.2.3 Other Eligibility Criteria Considerations

To assess any potential impact on patient eligibility with regard to safety, the investigator must refer to the IB for detailed information regarding warnings, precautions, contraindications, AEs, and other significant data pertaining to pamiparib being used in this study (BGB-290 Investigator's Brochure).

4.2.3.1 Patient Restrictions

The following restrictions may affect patient participation in this study:

- The investigator must be informed as soon as possible about any medications taken from the time of screening until the patient is discharged from the study
- In Phase 1 portion, patients will be required to fast for 2 hours before and 1 hour after pamiparib administration on all days throughout the study, water will be allowed freely. Grapefruit juice is not allowed throughout the study. No other dietary restrictions will apply
- In Phase 2 portion, patients will be instructed to swallow the capsules whole, in rapid succession, with water. Pamiparib can be administered with or without food based on the pamiparib food effect evaluation result

4.2.4 Patient Discontinuation and Withdrawal

Patients may withdraw at any time or be discontinued from the study at the discretion of the investigator should any untoward AEs occur. In addition, a patient may be withdrawn by the investigator or the sponsor if he/she violates the study plan or for administrative and/or other safety reasons. The investigator or study coordinator must notify the sponsor immediately when a patient has been discontinued/withdrawn due to an AE. Any AE which is present at the time of

discontinuation/withdrawal should be followed in accordance with the safety requirements outlined in Section 7.4. In the event that a patient is prematurely discontinued from the study at any time due to an AE (as defined in Section 9.1) the procedures stated in Section 9 must be followed.

If a patient is prematurely discontinued from participation in the study for any reason, the investigator must make every effort to perform end of treatment (EOT) visit at the earliest day possible within 5 days of the last dose of pamiparib: physical examination, vital signs,12-lead ECG, hematology, biochemistry, and AE assessment. If the discontinuation is due to unresolved toxicities for more than 21 days (56 days for anemia), EOT visit should be conducted at the earliest day as possible within 5 days after permanent discontinuation is determined.

In the Phase 1 portion, in addition to the post-study assessments, if a DLT occurs, the investigator will obtain, when possible, a 4 mL blood sample for analysis of plasma pamiparib concentration.

Patients who discontinue or are withdrawn for any reason other than DLT during Cycle 1 will be considered for replacement after due consideration by the sponsor and/or SMC if the minimum number of patients needed for the evaluation of RP2D is not met.

4.2.4.1 Reasons for Permanent Discontinuation of Pamiparib

The reason for discontinuation of pamiparib will be recorded in the electronic case report form (eCRF). These reasons include:

- PD
- AE
- Pregnancy
- Protocol violation
- Patient withdrew consent for study treatment
 - o Patients may voluntarily withdraw consent from study treatment at any time
 - Patients should continue to participate in the follow-up phase, if a patient withdraws consent from the treatment phase only
- Investigator's discretion
- Start of other anti-cancer therapy

4.2.4.2 End of Treatment Visit

The end of treatment (EOT) visit should occur within 5 days after pamiparib has been permanently discontinued. Required assessments are listed in Table 5 for Phase 1 and Table 7 for Phase 2. The visit at which tumor assessments showed PD may be used as the EOT visit as long as all required assessments were performed. Tumor assessments do not have to be repeated if they were performed at a prior response evaluation that documented PD. For the other required assessments, if they were performed within 4 days of the EOT visit, they do not need to be repeated on EOT visit. ECG does not have to be repeated if it was performed within 14 days of the EOT visit.

5 STUDY TREATMENTS

5.1 Description of Pamiparib

Patients will receive pamiparib as 10 mg capsules, or 40 mg capsules, or 40 mg capsules, depending on the dose level for Phase 1.

Patients will receive pamiparib as 20 mg rich capsules for Phase 2.

5.2 Dosage and Administration

Phase 1 Portion

The pamiparib will be taken once on Day 1 of Cycle 1 (morning only), followed by a 1-day treatment-free period (Day 2). Regular daily administration of pamiparib will commence on the morning of Day 3 of Cycle 1, as a 21-day period of repeated drug administration (Days 3 to 23). During subsequent cycles, the patients will take pamiparib BID from Day 1 to Day 21 (with no treatment-free or rest period).

Patients will be required to fast for at least 2 hours before and 1 hour after each administration of pamiparib throughout the study.

Phase 2 Portion

The patients will take pamiparib at 60 mg BID daily from Day 1 of Cycle 1 (with no treatment-free or rest period). Pamiparib capsules will be administered PO BID, once in the morning and once in the evening. The time difference between two consecutive doses will be approximately 12 hours with a window of ± 4 hours. Patients will be instructed to swallow the capsules whole, in rapid succession, with water. Pamiparib can be administered with or without food. However, to reduce gastrointestinal irritation that parmiparib may cause, patients are encouraged to take parmiparib with food.

A dose of pamiparib should be skipped if it is not taken within the upper range of the scheduled time, ie, within 16 hours. An extra dose of pamiparib should not be taken to make up for a missed dose. If vomiting occurs during the course of treatment, no re-dosing of the patient is allowed before the next scheduled dose.

On days with PK assessments, the morning dose of pamiparib should be administered in the clinic in accordance with the schedule for the PK samples.

The toxicity-related treatment delay must be agreed upon by the investigator and the sponsor Medical Monitor.

5.2.1 Treatment interruption and treatment discontinuation

All dose modifications should be based on the worst preceding toxicity. Generally, all dose interruptions or treatment discontinuation will be based on investigational drug-related AEs. For

reasons other than drug-related AEs, eg, safety concerns due to the poor health condition, if deemed necessary by the investigators, dose modifications could be applied after discussion with medical monitor.

Each patient is only allowed up to 2 dose reductions. In addition, a patient must discontinue treatment with pamiparib if, after treatment is resumed at a lower dose, the toxicity recurs with the same or worse severity.

Toxicity		Recommended Dose Modification ^a			
Hematologic					
Anemia (hemoglobin, Hgb)					
Hgb < 9.0 g/dL		 First occurrence of Hgb < 9.0 g/dL: Hold pamiparib and treat as medically indicated to get Hgb to ≥ 9 g/dL, and then ↓ pamiparib by 1 dose level to 40 mg BID 			
Grade 2 (8 ≤ Hgb <10	$9 \le Hgb < 10$ g/dL	• Continue dosing at current dose level and treat with appropriate supportive care as medically indicated			
g/dL)	$8 \le Hgb < 9 g/dL$	 Subsequent occurrence following dose reduction for anemia: Continue pamiparib without interruption with appropriate supportive care based on clinical assessment OR Hold pamiparib and treat as medically indicated to get Hgb to ≥ 9 g/dL, then restart at reduced dose level OR Hold pamiparib and treat as medically indicated to get Hgb to ≥ 9 g/dL, then √ pamiparib by 1 additional dose level to 20 mg BID 			
Grade 3 (Hgb < 8 g/dL)		 Subsequent occurrence following dose reduction for anemia: Continue pamiparib without interruption with appropriate supportive care based on clinical assessment OR Hold pamiparib and treat as medically indicated to get Hgb to ≥ 9 g/dL, then restart at reduced dose level OR Hold pamiparib and treat as medically indicated to get Hgb to ≥ 9 g/dL, then √ pamiparib by 1 additional dose level to 20 mg 			

BID

Table 9.	Criteria for interruption and re-initiation of Pamiparib due to treatment
associated ad	verse event

Toxicity	Recommended Dose Modification ^a
Grade 4 (life-threatening consequences; urgent intervention indicated)	 Second occurrence following dose reduction for anemia: Hold pamiparib and treat as medically indicated to get Hgb to ≥ 9 g/dL, then ↓ pamiparib by 1 additional dose level to 20 mg BID Third occurrence following 2 dose reductions for anemia: Discontinue pamiparib if anemia is not caused by any other confounding event, eg GI hemorrhage. Hold pamiparib and treat as medically indicated to get Hgb to ≥ 9 g/dL, then restart at reduced dose level.
 higher anemia, hematolog 2) For any patients showing explanation such as gastro 3) Dose increase can be considered 	should be done for the first 3 cycles during the study. For all Grade 2 or gy test should be done weekly thereafter until adequate recovery. Hgb dropping > 2 g/dL especially within a short time without alternative pointestinal bleeding, ψ pamiparib by 1 dose level should be considered sidered in certain cases, depending on approval from the medical monitor, naintained above 9 g/dL for at least 3 months
Neutropenia (absolute neutroph	il count, ANC)
Grade 3 (ANC <1.0 - 0.5 × 10 ⁹ /L)	 Hold pamiparib until resolved to Grade ≤2 or baseline If resolved ≤7 days, then maintain dose levels If resolved >7 days, then ↓ pamiparib by 1 dose level
Grade 4 (ANC $< 0.5 \times 10^{9}/L$)	Hold pamiparib until resolved to Grade ≤ 1 or baseline and ψ pamiparib by 1 dose level
Febrile neutropenia (ANC $<1.0 \times 10^{9}$ /L with single temperature of >38.3°C or sustained temperature of \geq 38°C for >1 hour)	Hold pamiparib until resolved and ↓ pamiparib by 1 dose level
Thrombocytopenia (platelet cou	unt, PLT)
Grade 3 (PLT <50 - 25 × 10 ⁹ /L)	 Hold pamiparib until resolved to Grade ≤1 or baseline If resolved ≤7 days, then maintain dose levels If resolved >7 days, then ↓ pamiparib by 1 dose level
Grade 4 (PLT $<25 \times 10^{9}/L$)	Hold pamiparib until resolved to Grade ≤1 or baseline and ↓ pamiparib by 1 dose level

Toxicity	Recommended Dose Modification ^a			
Renal				
Estimated glomerular filtration rate (CKD-EPI EQ; Appendix 6)				
If $\geq 60 \text{ mL/min}/1.73 \text{ m}^2$ at baseline: <30 to 15 mL/min/1.73 m ² or If <60 mL/min/1.73 m ² at baseline: $\geq 50\%$ reduction from baseline	 Hold pamiparib until resolved to ≥60 mL/min/1.73 m² If resolved ≤7 days, then maintain dose levels If resolved >7 days, then ↓ pamiparib by 1 dose level 			
Regardless of baseline: <15 mL/min/1.73 m ²	Permanently discontinue pamiparib			
Hepatic				
Bilirubin				
Grade 2 (>1.5 - 3.0 × ULN) Only applies to patients with normal bilirubin at baseline	 Hold pamiparib until resolved to Grade ≤1 or baseline If resolved ≤7 days, then maintain dose levels If resolved >7 days, then ↓ pamiparib by 1 dose level 			
Grade 3 (>3.0 - 10.0 × ULN)	 Hold pamiparib until resolved to Grade ≤1 or baseline If resolved ≤7 days, then maintain dose levels If resolved >7 days, then ↓ pamiparib by 1 dose level 			
Grade 4 (>10.0 × ULN)	Permanently discontinue pamiparib Note: If Grade 3 or 4 hyperbilirubinemia is due to the indirect (unconjugated) component only, and hemolysis as the etiology has been ruled out as per institutional guidelines (eg, review of peripheral blood smear and haptoglobin determination), then ψ pamiparib by 1 dose level and continue treatment at the discretion of the investigator in discussion with the medical monitor			
Aspartate aminotransferase (AS	oT) and/or alanine aminotransferase (ALT)			
Grade 3 (>5 and ≤20 × ULN)	 Hold pamiparib until AST and/or ALT resolved to ≤5 × ULN or baseline If ≤5 × ULN within 14 days, then ↓ pamiparib by 1 dose level If second episode, permanently discontinue pamiparib If persistent for >14 days, permanently discontinue pamiparib 			
Grade 4 (>20 × ULN)	Permanently discontinue pamiparib			

Toxicity	Recommended Dose Modification ^a
Pancreatic	
Pancreatitis	
Grade 3 or 4	Permanently discontinue pamiparib
Cardiac	
Cardiac - Prolonged QTc interv	al
QTcF >500 msec A change in QTc interval >60 msec from baseline or pre-dose value of whichever is the highest Cardiac - General	 Obtain triplicate ECGs (2 to 3 minutes apart) ~1 hour after initial ECG If mean QTcF >500 msec, or a change in QTc interval >60 msec from baseline, hold pamiparib until evaluation of ECGs by cardiologist Cardiology evaluation as soon as practical but within 7 days of initial abnormal ECG If mean QTcF >500 msec, or a change in QTc interval >60 msec from baseline confirmed by cardiologist, permanently discontinue pamiparib
Grade 3	Hold pamiparib until resolved to Grade ≤ 1 or baseline and Ψ pamiparib by 1 dose level
Grade 4	Permanently discontinue pamiparib
Other AEs	
Grade 3	Hold pamiparib until resolved to Grade ≤ 1 or baseline and ψ pamiparib by 1 dose level No dose reduction required for asymptomatic laboratory abnormalities
Grade 4 (>20 × ULN)	Permanently discontinue pamiparib

Abbreviations: AE, adverse event; ALT, alanine aminotransferase; ANC, absolute neutrophil count; AST, aspartate aminotransferase; CKD-EPI EQ: Chronic Kidney Disease Epidemiology Collaboration Equation; ECG, electrocardiogram; Hgb, hemoglobin; PLT, platelet (count); QTc, QT interval corrected for heart rate; QTcF, QT interval corrected for heart rate using Fridericia's formula; ULN, upper limit of normal.

For Phase 2 portion, the dose level of pamiparib is 60 mg BID (level 1), 40mg BID (level -1) and 20mg BID (level -2). Reescalation using intermediate doses may be possible providing tolerability is good, please contact sponsor medical monitor for discussion.

In the event of a DLT (see Table 4), treatment will be stopped and supportive therapy administered as required. If the toxicity resolves or subsides to Grade 0, Grade 1 or Grade 2 (Grade 2 is only applicable to neutropenia) within 14 days and interruption or delay of treatment for no more than 21 days of the onset of the DLT and the patient is showing clinical benefit in the investigator's opinion, resumption of treatment after resolution of a DLT will be at the next lower dose level tested

(or 50% lower if the DLT occurs with the first dose level). If the toxicity does not resolve to Grade 0, Grade 1 or Grade 2 (Grade 2 is only applicable to neutropenia) within 14 days of onset, the patient must be withdrawn from the study. Any exception to this must be agreed upon by the investigator and the medical monitor.

For management and follow-up of toxicity also refer to Section 4.1.3.

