4.1.2.1 Safety, Tolerability and Efficacy

Phase 2 portion will investigate efficacy in patients with selected tumor types and further evaluate safety and tolerability of pamiparib at 60 mg BID.

Patients will be monitored for safety, tolerability, and efficacy throughout the study. Radiological assessment of tumor response status should be performed approximately once every 6 weeks \pm 7 days for the first 18 weeks, thereafter once every 9 weeks \pm 7 days for the remaining period in the first year, and then once every 12 weeks \pm 7 days starting with the second year. For patients with first a response as complete response (CR) or partial response (PR), a response confirmation will need to be performed during the following 4-6 weeks, then patients will keep original tumor assessments schedule per protocol.

Tumor response will be assessed by IRR and investigators separately based on RECIST, version 1.1.

Patients will continue treatment until occurrence of unacceptable toxicities, disease progression, withdrawal of consent, investigator discretion, or delay of treatment due to unresolved toxicities for more than 21 days. Dose interruption due to investigational drug-related anemia could be on hold for up to 56 days consecutively.

Assessments ⁷	Pre- screening ¹	Screening ¹	Cycle 1 (21 days)	Cycle 2 (21 days)	Cycle 3 and subsequent Cycles (every 21 days for one cycle)	Unscheduled Visit ²	EOT Visit ³	Safety Follow-up ⁴	Survival Follow- up ⁵
Day of Study	Before screening	D -21 to -1	D1	D22	D43~	Varies	Within 5 days after	30 ± 5 days after last	Every 12 weeks
Allowed time window				±3 days	±3 days		last dose	dose	±7 days
Informed consent	Х	Х							
Baseline demographics		Х							
Medical history/treatment history ⁶		х							
Concurrent medications		Х	Х	Х	Х	Х	Х	Х	
Physical examination ⁸		Х	Х	Х	Х	Х	Х		
Vital signs		X	Х	Х	Х	Х	Х		
Height		X							
Weight		X				Х	Х		
ECOG performance status		X	Х	Х	X	Х	Х		
Hematology ⁹		-7 to -1 X	Х	X	x	Х	Х		
Clinical chemistry ⁹		-7 to -1 X	Х	Х	X	Х	Х		

1.0

Assessments ⁷	Pre- screening ¹	Screening ¹	Cycle 1 (21 days)	Cycle 2 (21 days)	Cycle 3 and subsequent Cycles (every 21 days for one cycle)	Unscheduled Visit ²	EOT Visit ³	Safety Follow-up⁴	Survival Follow- up ⁵
Day of Study	Before screening	D -21 to -1	D1	D22	D43~	Varies	Within 5 days after	30 ± 5 days after last	Every 12 weeks
Allowed time window				±3 days	±3 days		last dose	dose	±7 days

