3. EOT visit should be conducted at the earliest day as possible within 5 days of the last dose of pamiparib, if possible. If discontinuation is due to unresolved toxicities for more than 21 days (56 days for anemia), EOT visit should be conducted at the earliest day as possible within 5 days after permanent discontinuation is determined. The CT/MRI does not have to be repeated if it was performed at a prior response evaluation that documented progressive disease. CA-125 and ECG do not have to be repeated if it was performed within 14 days of the EOT visit, For the other required assessment, if they were performed within 4 days of the EOT visit, they do not need to be repeated on EOT visit

- 4. Approximately 30 days after the last day of pamiparib, a safety follow-up visit will occur with the outlined safety assessments. If a new anti-cancer therapy is initiated before this safety follow-up, a safety follow-up should be scheduled as soon as possible ideally before other anti-cancer treatment starts. For patients who do not want to or cannot return to the clinic for the safety follow-up, the patient should be contacted by phone for a review of AEs. If discontinuation is due to unresolved toxicities for more than 21 days, safety follow-up could be scheduled 30 ± 5 days after the last dose of treatment. If discontinuation is due to unresolved toxicities for more than 56 days for anemia, safety follow-up could be scheduled at the earliest day possible within 5 days after permanent discontinuation is determined
- 5. Patients will be followed for survival via phone contact approximately every 12 weeks \pm 7 days or as otherwise directed by the sponsor
- 6. Date of and response to last platinum treatment must be documented (unless no platinum treatment has been received). Patients are defined as platinum-sensitive if disease progression by RECIST or CA-125 criteria had occurred ≥ 6 months after their last dose of platinum treatment while platinum-resistant is defined as disease progression that occurred < 6 months after the last dose of platinum
- 7. All assessments, unless stated otherwise, must be performed before investigational product administration in each cycle
- Full physical examination includes the following items: 1) general appearance; 2) head, eyes, ears, nose and throat; 3) neck; 4) heart; 5) chest (including lungs); 6) abdomen;

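### Protocol 5.2.1 requires stopping when a toxicity recurs at the same or worse severity after dose reduction, but Table 9 keeps such anemia recurrences on pamiparib; separately, the renal restart level exceeds every baseline in its own <60 stratum

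*Protocol*

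**What the plan says.** **General rule.** Protocol 5.2.1 allows at most two dose reductions and adds that "a patient must discontinue treatment with pamiparib if, after treatment is resumed at a lower dose, the toxicity recurs with the same or worse severity". No toxicity is exempted.

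**Anemia rows of Table 9 (same section).** The column is headed "Recommended Dose Modification".
- First Hgb below 9.0 g/dL: hold, recover to at least 9, restart at 40 mg BID.
- Grade 2 with Hgb 9 to <10: stay at the current dose with supportive care.
- Hgb 8 to <9, or Grade 3, after an earlier reduction for anemia: three alternatives. The first is "Continue pamiparib without interruption with appropriate supportive care based on clinical assessment"; the others are hold and restart at the reduced dose, or hold and step down to 20 mg BID.
- Grade 4: "Second occurrence following dose reduction for anemia: Hold pamiparib and treat as medically indicated to get Hgb to" at least 9 g/dL, then 20 mg BID. At a third occurrence, after two reductions: "Discontinue pamiparib if anemia is not caused by any other confounding event, eg GI hemorrhage".

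**Time limits.** Protocol 4.1.2.1 lists among the reasons for ending treatment "withdrawal of consent, investigator discretion, or delay of treatment due to unresolved toxicities for more than 21 days", and then says "Dose interruption due to investigational drug-related anemia could be on hold for up to 56 days consecutively". Table 7 footnote 3 carries the same 21-day and 56-day limits.

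**Renal row of Table 9.** There are two hold triggers: a fall to between 15 and <30 from a baseline eGFR of 60 or more, and a fall of at least 50% from a baseline below 60. Both share one restart level, 60 or above. Below 15, treatment stops permanently. Section 4.2.1 admits patients from eGFR 30.

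**The concern.** A site facing recurrent anemia after a dose reduction gets two incompatible instructions from one section. Stopping complies: 5.2.1 requires it, Table 9 only recommends, and 4.2.4.1 accepts an AE or investigator's discretion as a reason. Following Table 9 breaches a sentence worded as mandatory. Comparable patients could therefore be stopped at one site and continued at another, and the Version 5.0 anemia algorithm cannot be followed for them without a deviation from 5.2.1.

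The SAP plans descriptive work that touches this. Section 6.7 and Appendix 10.2 compare hematological safety, exposure and dose modification before and after the amendment, and 6.7 tabulates efficacy by most recent prescribed dose. If sites resolve the conflict differently, part of what those tables show will be site interpretation.

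The renal problem concerns individual patients: someone whose kidney function has returned fully to its starting value may have no written route back to treatment.

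**Working it through.** The plan gives no figure on this point, so the anemia check sets the rules side by side and the renal check is simple arithmetic.

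**Anemia.** Inputs: the 5.2.1 sentence; the Table 9 anemia rows; severity read as CTCAE grade, as section 9.1.2 prescribes. Each patient below had a first Hgb below 9.0, was held, recovered and restarted at 40 mg BID.

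| First event | Recurrence | 5.2.1 | Table 9 | Conflict |
|---|---|---|---|---|
| 8 to <9 (Grade 2) | 9 to <10 (Grade 2) | same grade: stop | continue at current dose | yes, by grade |
| 8 to <9 (Grade 2) | 8 to <9 (Grade 2) | same: stop | continue, restart, or 20 mg BID | yes |
| 8 to <9 (Grade 2) | Grade 3 | worse: stop | continue, restart, or 20 mg BID | yes |
| Grade 3 | Grade 3 | same: stop | continue, restart, or 20 mg BID | yes |
| Any | Grade 4, second occurrence | same or worse: stop | hold, then 20 mg BID | yes |
| Grade 3 or 4 | a lower grade | milder: rule not triggered | stays on drug | no |

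The rows illustrate the logic; they do not count patients. Two situations lie outside the conflict. A patient whose anemia hold exceeds 56 days is discontinued and never restarts, so the 5.2.1 condition is not met. At a third Grade 4 event Table 9 also discontinues, unless another event explains the anemia.

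**Renal.** Inputs: baseline b from 30 (section 4.2.1) to just under 60; hold when eGFR is at or below b/2; permanent stop below 15; restart at 60 or above (Table 9). The hold band therefore runs from 15 to b/2. The shortfall after complete recovery is 60 − b, and the restart level relative to baseline is 60/b.

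| Baseline b | Hold band (15 to b/2) | 60 − b | 60/b |
|---|---|---|---|
| 30 | 15 only | 30 | 200% |
| 40 | 15 to 20 | 20 | 150% |
| 50 | 15 to 25 | 10 | 120% |
| 59 | 15 to 29.5 | 1 | 102% |

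Sixty is above every baseline in the stratum, so return to baseline never meets the restart level. The graded neutropenia, thrombocytopenia, bilirubin and AST/ALT hold rules all accept baseline as an alternative; the renal row does not.

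**The case against.** The best defence is that Table 9 plainly governs. Its anemia rows are the specific provision, were revised in Version 5.0, and are written for recurrence after a reduction. SAP 6.7 describes that amendment as aimed mainly at dose modification and hematology monitoring. Where the table's authors wanted a recurrence stop they wrote one: the AST/ALT row discontinues at a second episode. Read literally by grade, 5.2.1 would end treatment for a recurrence at Hgb 9.5, above both Table 9's restart level and the entry floor of 9. All of this stands as evidence of intent. It does not cure the text, because nothing gives the table precedence and the general sentence is the mandatory one.

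A second defence is sponsor oversight. Section 5.2 requires toxicity-related delays to be agreed with the Medical Monitor, which should limit variation between sites. It covers holds, not the option to continue without interruption. The provision for agreed exceptions that follows Table 9 belongs to the DLT paragraph, not to this rule.

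On the renal row, the hold band is narrow, and accepting baseline is not universal in the table: febrile neutropenia is held only until resolved. A reader might also infer that these patients are certain to be discontinued at day 21. The documents do not support that. The limit applies to unresolved toxicities, and whether a patient back at baseline still has one is arguable. The limit may end treatment.

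**Conclusion.** Wrong as written, and worth fixing. The anemia conflict is a direct contradiction between a mandatory sentence and the table beside it, confined to recurrences of the same or worse severity after restart at a lower dose. Including Hgb 9 to <10 after a first event at 8 to <9 depends on reading severity as CTCAE grade; the other conflicting rows do not. The renal gap is separate and lesser.

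Neither part can be sized in patients. A reader might take the Grade 3 anemia counts in section 1.4.3 as a measure, but they are pooled over doses and say nothing about recurrence after reduction. Nor should one infer that every anemia recurrence conflicts, or that the mandatory sentence must be the intended rule; the evidence of intent points to Table 9. It would also go too far to say that the primary analysis is compromised: the exact ORR test and its stated power use none of these rules and are unaffected.

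**What to change.** 1. In 5.2.1, add to the end of the recurrence sentence: *except anemia, which is managed per Table 9*. The downside is that no recurrence stop then remains for Grade 2 or Grade 3 anemia, however often it returns, beyond the 56-day hold limit and investigator discretion. The clinical team should confirm that this is intended.
2. In the renal row, add *or baseline* after the restart level of 60 mL/min/1.73 m² for patients with baseline below 60. For baselines of 60 or more the restart level stays at 60.

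The cost is a short protocol amendment (one clause and two words), the IEC/IRB review that section 11.2 describes for amended protocols, and a memo to sites. No new data, visits or procedures are needed.
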